- If the platelet count drops to $\geq 50,000$ but $\leq 100,000$ /mm 3 while on the reduced dose of 3.5 million units twice daily, rIL2 will be discontinued until the platelet count reaches 100,000/mm 3 and then resumed at a dose of 2 million units twice daily. If the platelet count then remains above 100,000 /mm 3 , this dose will be continued until the end of study. If the platelet count falls again to $\leq 100,000$ /mm 3 while on the reduced 2 million unit twice daily dose, rIL2 will be permanently discontinued.
- Should the platelet count decrease to $< 50,000$ /mm 3 , rIL-2 will be permanently discontinued.

E.1.5. AST and ALT Abnormalities

Participants who develop AST or ALT elevations will be referred for treatment by a qualified healthcare professional. Volunteers with AST or ALT levels $> 2.5 \times$ ULN at screening will be excluded.

- Volunteers with cirrhosis, severe liver disease, or active hepatitis B or C infection will be excluded from the study.
- Should AST or ALT values rise to $> 3 \times$ ULN, rIL-2 will be interrupted. rIL-2 may be resumed at 3.5 million units twice daily when AST or ALT fall to $< 2 \times$ ULN. If AST and ALT values then remain below $3 \times$ ULN, this dose will be continued to the end of study.
- If AST or ALT values rise again to $> 3 \times$ ULN while on the reduced dose of 3.5 million units twice daily, rIL-2 will be interrupted until AST and ALT fall to $< 2 \times$ ULN and then resumed at a dose of 2 million units twice daily. If AST and ALT values then remain below $3 \times$ ULN, this dose will be continued to the end of study. If AST or ALT levels rise again to $> 3 \times$ ULN while on the reduced 2 million unit twice daily dose, rIL2 will be permanently discontinued.
- If ALT values rise again to $> 3 \times$ ULN while the patient is receiving 2 million units twice daily, rIL-2 will be discontinued permanently.
- Should AST or ALT values rise to $> 5 \times$ ULN, rIL2 will be permanently discontinued.

E.1.6. Thyroid Test Abnormalities

Participants who develop thyroid function test (TFT) abnormalities will be referred for treatment by a qualified healthcare professional. Volunteers with abnormal TFTs or levels of anti-thyroid antibodies (anti-Tpo) at screening will be excluded.

- If a participant develops a TSH level $> 3.98 \text{ mIU/L}$, rIL-2 will be permanently discontinued.
- If T3 or T4 levels are outside the normal reference range of the laboratory, rIL-2 will be permanently discontinued.

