 - Lymphoma, primary of brain
 - Progressive multifocal leukoencephalopathy
 - Toxoplasmosis of brain
- Occurrence of herpes zoster reactivation involving more than two dermatomes or visceral involvement including but not limited to viral pneumonia, encephalitis and hepatitis.
- Occurrence of a serious infection that is considered life-threatening or requires inpatient treatment.
- Occurrence of an incident cancer other than a localized basal cell carcinoma of the skin that requires local excision only.
- Requirement for prohibited concomitant medications (see exclusion criteria and section C.6).
- Pregnancy or breastfeeding.
- Deep vein thrombosis or pulmonary embolism.
- Myocardial infarction or other acute coronary syndrome.
- Development of a grade ≥ 3 hypersensitivity reaction, OR a grade 2 hypersensitivity reaction that includes manifestations of angioedema, or suspected or confirmed capillary leak syndrome.
- Development of an ANC < 500 cells/mm³.
- Development of a platelet count $< 50,000$ /mm³.
- Elevation of AST or ALT to > 5 x ULN.
- Serum TSH elevation to ≥ 3.99 mIU/L, abnormal serum T4 or T3 levels, abnormal levels of anti-Tpo antibodies, or symptomatic hypo- or hyperthyroidism.
- Completion of treatment as defined in the protocol.
- Request by participant or his/her healthcare providers to terminate treatment.
- Reasons believed to be clinically significant by the investigators, even if not addressed in the adverse event management section of the protocol.

F.2. PREMATURE STUDY DISCONTINUATION

- Failure by the participant to attend 3 consecutive visits.
- Request by participant or his/her healthcare providers to terminate participation in the study.
- Participant judged by the investigator to be at significant risk of failing to comply with the provisions of the protocol as to cause harm to self or seriously interfere with the validity of the study results.
- At the discretion of the institutional review board (IRB), Office for Human Research Protections (OHRP), FDA, NIAID or investigator.

F.3. TEMPORARY TREATMENT DISCONTINUATION

- Criteria for withholding dose met (refer to section C.5.2 and to Manual of Operations).

G. SAFETY MONITORING

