I.6.1.3. Risk Mitigation Strategy for Thromboembolic Disease

In the ESPRIT trial but not among participants in the SILCAAT trial, there was an increased occurrence of vascular events (but not in cardiac disorders) that were seen among 40 of 466 patients receiving IL-2 plus ART and 14 of 386 receiving ART alone. The most frequent vascular event was deep vein thrombosis seen in 10 IL-2 plus ART recipients and in 2 ART alone recipients. To mitigate risk for vascular events in this trial, persons with a history of venous thrombosis will be excluded from participation and at each visit, signs and symptoms of venous thrombosis will be sought.

I.6.1.4. Risk Mitigation Strategy for Laboratory Abnormalities

I.6.1.4.1. Neutropenia

The risk mitigation plan for neutropenia includes:

- Participants with an ANC <1500 cells/mm³ will not be permitted to enroll in the study;
- ANC will be measured at each clinic visit
- Should the ANC decrease to ≥500 but ≤1,000 cells/mm³, the rIL-2 dose will be interrupted until the ANC is >1,000 cells/mm³ and then rIL-2 will be restarted at 3.5 million units twice daily. If the ANC remains above 1,000 cells/mm³, this dose will be continued until the end of the study.
- Should the ANC decrease ≥500 but ≤1,000 cells/mm³ while on the reduced dose of 3.5 million units twice daily, rIL2 will be discontinued until the ANC reaches 1,000 cells/mm³, and then resumed at a dose of 2 million units twice daily. If the ANC then remains above 1,000 cells/mm³, this dose will be continued until the end of study. If the ANC falls again to ≤1,000 cells/mm³ while on the reduced 2 million unit twice daily dose, rIL2 will be permanently discontinued.
- Should the ANC decrease to <500 cells/mm³, rIL_2 will be discontinued.

I.6.1.4.2. Thrombocytopenia

The risk mitigation plan for thrombocytopenia includes:

- Participants with a platelet count <150,000/mm³ will not be enrolled in the study;
- Platelet counts will be measured at each clinic visit;
- Should the platelet count decrease to ≥50,000 but ≤100,000/mm³ the rIL-2 dose will be interrupted until the platelet count is >100,000/mm³ and then IL-2 will be restarted at 3.5 million units twice daily. If the platelet count remains above 100,000 /mm³, this dose will continue until the end of the study.

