- Should the platelet count drop to ≥50,000 but ≤100,000/mm³ while on the reduced dose of 3.5 million units twice daily, rIL2 will be discontinued until the platelet count reaches 100,000/mm³ and then rIL-2 will be restarted at 2 million units twice daily. If the platelet count remains above 100,000/ mm³, this dose will be continued until the end of the study. If the platelet count falls again to ≤100,000/mm³ while on the reduced 2 million units twice daily, rIL2 will be permanently discontinued.
- Should the platelet count decrease to <50,000/mm³ ,rIL-2 will be discontinued.

I.6.1.4.3. AST and ALT Abnormalities

The risk mitigation plan for AST or ALT abnormalities includes:

- Participants with an AST or ALT $\geq 2.5 \times$ ULN will be excluded from the study.
- Patients with cirrhosis, severe liver disease or active or chronic hepatitis B or C infection will be excluded from the study.
- AST and ALT will be evaluated at each clinic visit.
- For AST or ALT values $> 3 \times$ ULN, the rIL-2 will be discontinued. rIL-2 may be resumed at 3.5 million units twice daily when AST or ALT fall to $< 2 \times$ ULN. If AST and ALT values then remain below $3 \times$ ULN, this dose will be continued until the end of the study.
- If AST or ALT values rise again to $> 3 \times$ ULN while on the reduced dose of 3.5 million units twice daily, rIL-2 will be discontinued until AST and ALT fall to $< 2 \times$ ULN and then resumed at a dose of 2 million units twice daily. If AST and ALT values then remain below $3 \times$ ULN, this dose will be continued until the end of the study.
- If ALT values rise again to $> 3 \times$ ULN while the patient is receiving 2 million units twice daily, rIL-2 will be discontinued permanently.

I.6.1.4.4. Thyroid Abnormalities

The risk mitigation strategy for thyroid abnormalities includes:

- Volunteers with abnormal thyroid function tests or elevated levels of anti-Tpo antibodies at screening will be excluded.
- Participants who develop symptomatic thyroid disease or abnormal T3 or T4 serum levels will be required to discontinue study treatment permanently.
- Participants who develop TSH levels $\geq 3.99 \text{ mIU/L}$ will be required to discontinue study treatment permanently.
- Participants who develop elevated anti-Tpo antibodies will be required to discontinue study treatment permanently.

I.6.1.4.5. Renal Dysfunction

The risk mitigation strategy for renal function abnormalities includes:

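### For AST or ALT above 5 x ULN, section I.6.1.4.3 lets rIL-2 resume while E.1.5 and F.1 stop it permanently, and no order of precedence is stated

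*Combined protocol and SAP*

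**What the plan says.** The protocol sets out rules for raised AST or ALT in three places.

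- **I.6.1.4.3 (human-subjects section, risk mitigation).** The list opens with "The risk mitigation plan for AST or ALT abnormalities includes". Above 3 times "ULN, the rIL-2 will be discontinued. rIL-2 may be resumed at 3.5 million units twice daily when AST or ALT fall to" less than 2 times ULN. After a second rise above 3 x ULN on that dose, treatment stops until both enzymes are below 2 times "ULN and then resumed at a dose of 2 million units twice daily. If AST and ALT values then remain below" 3 times ULN, that dose continues. The only permanent stop is for ALT that again exceeds 3 times "ULN while the patient is receiving 2 million units twice daily, rIL-2 will be discontinued permanently".
- **E.1.5 (management of specific adverse events).** The same steps appear above 3 x ULN. The permanent stop on the second reduced dose applies to AST or ALT, and an ALT-only version of it is then repeated. A last bullet adds that if AST or ALT rises above 5 times "ULN, rIL2 will be permanently discontinued".
- **F.1 (permanent treatment discontinuation).** The list of criteria includes "Elevation of AST or ALT to > 5 x ULN".

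**The concern.** I.6.1.4.3 is not merely silent about values above 5 x ULN. Its rule for values above 3 x ULN has no ceiling, so it covers a value of, say, 6 x ULN and attaches a route back to treatment. E.1.5 and F.1 close that route. I.7.2 presents the risk strategies set out above it as the ones implemented for the trial, so I.6 cannot be set aside as background.

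The first matter at stake is safety: a participant with a marked transaminase rise could be handled differently depending on which section is consulted. There is also a smaller consequence for the analysis. Under C.2.1 the on-treatment population consists of those who received all eight cycles, and a secondary model includes a term for the number of cycles received. A participant who resumes may still complete eight cycles; one stopped permanently before cycle 8 cannot. With 20 participants, each one is 1/20 = 5% of the enrolled sample.

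**Working it through.** No sample size, power or error rate is involved, so the check is a side-by-side reading of the three rule sets by enzyme value and dose level. The inputs are the bullets of I.6.1.4.3, those of E.1.5, and the AST/ALT line of F.1. Doses are those written in the protocol, each given twice daily.

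| AST/ALT value | Dose level | I.6.1.4.3 | E.1.5 and F.1 | Same? |
|---|---|---|---|---|
| Above 3, up to 5 x ULN | Starting (5 MIU) | Stop; may resume at 3.5 MIU once below 2 x ULN | E.1.5: the same; F.1 not triggered | Yes |
| Above 3, up to 5 x ULN | First reduced (3.5 MIU) | Stop; then resume at 2 MIU once below 2 x ULN | E.1.5: the same; F.1 not triggered | Yes |
| Above 3, up to 5 x ULN | Second reduced (2 MIU) | ALT: permanent stop. AST alone: no permanent stop stated | E.1.5: permanent stop for AST or ALT | ALT yes, AST no |
| Above 5 x ULN | Starting (5 MIU) | Stop; may resume at 3.5 MIU once below 2 x ULN | Permanent stop in both | **No** |
| Above 5 x ULN | First reduced (3.5 MIU) | Stop; then resume at 2 MIU once below 2 x ULN | Permanent stop in both | **No** |
| Above 5 x ULN | Second reduced (2 MIU) | ALT: permanent stop. AST alone: no permanent stop stated | Permanent stop in both | ALT yes, AST no |

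The disagreement has two parts. The main one is AST or ALT above 5 x ULN on the starting or first reduced dose. The lesser one is AST alone on the second reduced dose.

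The neighbouring subsections show what the liver subsection lacks:

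- I.6.1.4.1 limits its interrupt-and-restart band to an ANC of 500 to 1,000 and has a separate stop rule below 500.
- I.6.1.4.2 limits its band to platelets of 50,000 to 100,000 and has a separate stop rule below 50,000.
- I.6.1.4.5 limits its first interruption band to creatinine of at most 3 mg/dL and stops treatment permanently above that, as E.1.7 does.
- I.6.1.4.3 has neither an upper bound on its resume rule nor an outer stop.

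The documents contain no clause saying that sections E and F prevail over section I, or the reverse.

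**The case against.** The best answer is that the protocol already directs staff to the right place. C.5.2 says that criteria for specific adverse events are in E.1, E.2.2 sends readers to E.1 for dose modification, and F.1 is the dedicated list of permanent stops. Section G has the investigators review each event of grade 2 or higher in real time against the discontinuation criteria. Staff who follow these references reach the 5 x ULN stop. E.1.5 also words its own rule above 3 x ULN without a ceiling and relies on a later bullet to limit it, so F.1 could be read as limiting I.6.1.4.3 in the same way. The opening words of I.6.1.4.3 do not claim a complete list, and its first resumption is permissive. For AST alone on the lowest dose, the general rule in C.5.2, which ends treatment if that dose is not tolerated, might be applied.

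Much of this stands, and it lowers the chance of an error. It does not remove the conflict. In E.1.5 the limiting bullet is in the same list; in I.6.1.4.3 the reader must know to look elsewhere. The second-rise bullet directs resumption without the permissive wording used for the first. Routing references are not a precedence clause.

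Two stronger readings are tempting but not supported:

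- **A reader might infer that the ANC and platelet stops are weakened too.** I.6.1.4.1 and I.6.1.4.2 say only that treatment is discontinued below 500 and below 50,000, and the same verb serves for temporary holds ("rIL2 will be discontinued" until the count recovers). But each such hold carries a recovery condition and a restart dose, and the outer rules carry neither. They read naturally as final, in line with E.1.3, E.1.4 and F.1 ("Development of an ANC" below 500). Only the word *permanently* is missing.
- **A reader might infer that the IRB sees only the section I version.** I.1 says that the IRB reviews the protocol and the consent document, which takes in E.1.5 and F.1.

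**Conclusion.** The point holds for AST and ALT. Above 5 x ULN on the starting or first reduced dose, I.6.1.4.3 permits or directs resumption after a fall below 2 x ULN, while E.1.5 and F.1 stop treatment permanently. A lesser gap is that the last stop in I.6.1.4.3 omits AST. The ANC and platelet wording is a minor matter of consistency, not a contradiction.

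The number of participants affected cannot be derived, because the documents give no expected frequency of values above 5 x ULN; enrolment is at most 20. The conclusion assumes that the I.6.1.4 bullets are meant as instructions, which I.7.2 supports. It does not show that any participant would be re-dosed against F.1, since the cross-references make that less likely. It should be corrected because it is a conflict over a safety stop and is cheap to remove. Nothing here bears on which rule is clinically right.

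**What to change.** Have the sponsor confirm the intended rule, then do one of two things: reconcile I.6.1.4.3 with E.1.5 and F.1 at every value and dose level, including whether the stop on the second reduced dose covers AST as well as ALT; or replace the duplicated dose rules in I.6.1.4 with a cross-reference to E.1 and F.1. The cross-reference also prevents the copies from drifting apart at later amendments.

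In the same edit, align the wording for ANC below 500 and platelets below 50,000 in I.6.1.4.1 and I.6.1.4.2 with E.1.3, E.1.4 and F.1.

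The cost is protocol wording only, with no change to sample size, visits, assays or planned analyses.
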